#### **7.7.2.5.2 Expedited Reporting by the Sponsor to a Regulatory Health Authority**

Global Safety will monitor data for safety. The Sponsor will manage the expedited reporting of relevant safety information to concerned health authorities, competent authorities, and IRBs/IECs in accordance with local laws and regulations.

#### **7.7.2.6 Discontinuation, Treatment Interruption, and Unblinding of Blinded Treatment Due to Safety Observations**

##### **7.7.2.6.1 Discontinuation**

See **Section 7.3.3** for the criteria by which a subject must be discontinued. Should a subject be discontinued from the trial, complete the visit activities as specified for discontinuation in the Trial Flow Chart in **Section 2.2**.

##### **7.7.2.6.2 Temporary Interruption of Treatment for a Subject**

A Subject may not temporarily interrupt and then restart treatment. The investigator is to discontinue a subject as necessary according to the criteria provided in **Section 7.3.3**.

### **7.7.2.6.3 Modification of Dose and/or Administration of Investigational Product for a Subject**

The dose and administration to any subject may not be modified. If necessary a subject must be discontinued for the reasons described in **Section 7.3.3**.

### **7.7.2.6.4 Unblinding Treatment for a Subject During the Trial**

No treatments in this current trial are blinded.

## **7.7.3 Other Endpoints**

### **7.7.3.1 Primary endpoints**

- To correlate serum soluble ST2 levels with endoscopic activity of disease (assessed by endoscopy subscore of Mayo score) at week 6 in moderate to severe UC subjects under golimumab treatment.
- To correlate serum soluble ST2 levels with histological activity (assessed by Geboes index) at week 6 in moderate to severe UC subjects under golimumab treatment.

See **Section 7.7.2.2** for the definition of endoscopic and histological activity of disease.

### **7.7.3.2 Secondary endpoints**

- To correlate serum soluble ST2 levels with endoscopic activity (assessed by endoscopy subscore of Mayo score) at week 16 in moderate to severe UC subjects under golimumab treatment.
- To correlate serum soluble ST2 levels with histological activity (assessed by Geboes index) at week 16 in moderate to severe UC subjects under golimumab treatment.
- To correlate serum soluble ST2 levels with fecal calprotectin levels at week 6 and week 16.
- To correlate serum soluble ST2 levels with clinical activity (assessed by total Mayo score) at week 6 and week 16.

- To evaluate the potential of serum soluble ST2 as a predictor of endoscopic response to golimumab by comparing Mayo endoscopic activity (activity [subscore  $\geq$  2] or no activity [subscore 0 or 1]) with ST2 at baseline and change of ST2 between baseline and Week 6.
- To correlate serum soluble ST2 levels with maintenance of endoscopic response to golimumab by comparing subjects who achieved endoscopic response at week 6 [subscore 0 or 1] and maintained through week 16 versus subjects who did not maintain response throughout the same period, regarding serum soluble ST2 at baseline, week 6 and change between baseline and week 6.
- To correlate Mayo endoscopic score with UCEIS overall score at week 6 and week 16 in moderate to severe UC subjects under golimumab treatment.

#### 7.7.3.3 Exploratory endpoints

- To compare serum golimumab levels with clinical activity (total Mayo score) at weeks 6 and 16.
- To compare serum golimumab levels in subjects with endoscopic active disease (total Mayo score  $>2$ ) and subjects with inactive disease (total Mayo score  $\leq 2$  points with no individual subscore  $>1$ ) at week 6 and 16.
- To compare the presence of anti-golimumab antibodies (+ or -) and clinical activity (total Mayo score) at weeks 6 and 16.
- To compare the presence of anti-golimumab antibodies in subjects with endoscopic active disease (total Mayo score  $>2$ ) and subjects with inactive disease (total Mayo score  $\leq 2$  points with no individual subscore  $>1$ ) at week 6 and 16.
- To compare serum golimumab levels with endoscopic activity (endoscopic Mayo score) at weeks 6 and 16.
- To compare the presence of anti-golimumab antibodies (+ or -) and endoscopic activity (endoscopic Mayo score) at weeks 6 and 16.
- To compare serum golimumab levels with faecal calprotectin at weeks 6 and 16.
- To compare the presence of anti-golimumab antibodies (+ or -) and faecal calprotectin at weeks 6 and 16.
- To compare serum golimumab levels with histological activity (Geboes index) at weeks 6 and 16.
- To compare the presence of anti-golimumab antibodies (+ or -) and histological activity (Geboes index) at weeks 6 and 16.

- To compare quartile serum golimumab levels with rates of clinical response and clinical remission
- To compare serum golimumab levels between subjects who achieved response at week 6 and subjects who did not.
- To compare serum golimumab levels among subjects who achieved response at week 16 and subjects who did not.
- To compare the presence of anti-golimumab antibodies among subjects who achieved response at week 6 and subjects who did not.
- To compare the presence of anti-golimumab antibodies who achieved response at week 16 and subjects who did not.
- To compare serum golimumab levels between subjects who achieved remission at week 6 and subjects who did not.
- To compare serum golimumab levels among subjects who achieved remission at week 16 and subjects who did not.
- To compare the presence of anti-golimumab antibodies among subjects who achieved remission at week 6 and subjects who did not.
- To compare the presence of anti-golimumab antibodies who achieved remission at week 16 and subjects who did not.

See **Section 7.7.2.2** for the definitions of interest.

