#### 7.7.2.2 Definition of Terms

- Moderate to severe active UC is defined in this study as a total Mayo score of 6 to 12, inclusive.
- The total Mayo Score, is a scale for assessing UC activity, it is the sum of 4 subscores and has values that range from 0 to 12. It includes assessment of Stool frequency (0-3) + Rectal bleeding (0-3) + Physician's global assessment (0-3) + Findings of endoscopy (0-3). Clinical remission: ≤2 points with no individual subscore > 1 ; Mildly active disease: 3-5 points; Moderately active disease: 6-10 points; Severely active disease: 11-12 points
- Endoscopic Mayo score (0-3): 0 = Normal or inactive disease, 1 = Mild disease (erythema, decreased vascular pattern, mild friability); 2 = Moderate disease (marked erythema, absent vascular pattern, friability, erosions); 3 = Severe disease (spontaneous bleeding, ulceration) - See Appendix 3.

- Partial Mayo score: Mayo score excluding the endoscopy subscore and has values that range from 0 to 9.
- Mucosal healing in this study will be determined by the endoscopy subscore of the Mayo score. Mucosal healing corresponds to endoscopy subscore of 0 or 1.
- Geboes index, is a validated score for evaluating histologic disease activity in UC as follows: grade 0, structural and architectural changes; grade 1, chronic inflammatory infiltrate; grade 2, lamina propria neutrophils and eosinophils; grade 3, neutrophils in the epithelium; grade 4, crypt destruction; grade 5, erosions or ulceration ; a higher score indicating more severe disease. Active histologic disease can be defined as a Geboes score  $\geq 3.1$  (presence of epithelial neutrophils with or without crypt destruction or erosions) (Geboes et al., 2000). - See Appendix 5
- Ulcerative Colitis Endoscopic Index of Severity (UCEIS) is a 3-item (vascular pattern, bleeding and erosion/ulceration) validated tool for assessing endoscopic severity of UC. Each item with three or four levels of severity, yielding a 9-point scale that accounts for 94% of the variance between observers in the overall assessment of severity (Travis et al., 2011) - See Appendix 4
- Clinical response is defined as a reduction in the Mayo score of at least 3 points and a decrease of at least 30% from the baseline score, accompanied by a decrease of at least 1 point in the rectal bleeding scale or an absolute rectal bleeding score of 0 or 1.
- Clinical remission is defined as Mayo score  $\leq 2$ , with no individual subscore exceeding 1.

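### Two exploratory endpoints label a total-Mayo split, in effect non-remission versus remission, as endoscopic activity, and the rule leaves one score pattern unclassified

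*Combined protocol and SAP*

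**What the plan says.** All references are to the combined protocol and SAP.

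- **Section 7.7.3.3, the two bullets.** One reads "To compare serum golimumab levels in subjects with endoscopic active disease (total Mayo score" above 2) and the other "To compare the presence of anti-golimumab antibodies in subjects with endoscopic active disease (total Mayo score" above 2). Each compares that group, at weeks 6 and 16, with subjects whose disease is called inactive: total Mayo of 2 or less and no subscore above 1.
- **Section 7.7.3.3, neighbouring bullets.** The bullet just before the first of the two is "To compare serum golimumab levels with clinical activity (total Mayo score) at weeks 6 and 16". The endoscopic bullets begin only after both, with "To compare serum golimumab levels with endoscopic activity (endoscopic Mayo score) at weeks 6 and 16". The section closes by sending the reader to Section 7.7.2.2 "for the definitions of interest".
- **Section 7.7.2.2.** Clinical remission is a total Mayo of 2 or less "with no individual subscore exceeding 1". Totals above 2 are graded "Mildly active disease: 3-5 points; Moderately active disease: 6-10 points; Severely active disease: 11-12 points". On the endoscopic scale, "Mucosal healing corresponds to endoscopy subscore of 0 or 1".
- **Section 7.7.3.2.** For ST2 as a predictor of endoscopic response, activity is an endoscopy subscore of 2 or more and no activity is 0 or 1.
- **Section 8.0.** The two exploratory comparisons appear with the same total-Mayo cut-offs and visits, but the groups are called only active and inactive disease. Levels are compared by t-test or Mann-Whitney, and antibodies by Chi-Square or Fisher. Separate bullets relate levels and antibodies to the 0-3 endoscopic score, and compare subjects in remission with those who are not.

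**The concern.** The label and the rule describe different things. The rule sums stool frequency, rectal bleeding, physician's global assessment and endoscopy, so a subject can exceed 2 on the first three with a normal mucosa. The label says the split is endoscopic. If results are reported under the endpoint wording, a contrast that is very nearly non-remission versus remission will be read as drug exposure and immunogenicity by endoscopic status. In a study whose purpose is to keep clinical, endoscopic and histological activity apart, that is the distinction that should not blur. The same result would also look like endoscopic evidence separate from the remission comparison, which it almost duplicates.

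There is a second, smaller defect. The two groups are not complementary, so some subjects have no group under either section.

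**Working it through.** The plan gives no figure of its own here, so the check is a comparison of definitions followed by a count.

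**Definitions side by side**

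| Place | Term | Score used | Split |
|---|---|---|---|
| 7.7.3.3, two bullets | endoscopic active vs inactive | total Mayo | >2 vs ≤2 with no subscore >1 |
| 8.0, matching bullets | active vs inactive | total Mayo | same |
| 7.7.2.2 | clinical remission | total Mayo | ≤2 with no subscore >1 |
| 7.7.2.2 | mucosal healing | endoscopy subscore | 0 or 1 |
| 7.7.3.2 | endoscopic activity | endoscopy subscore | ≥2 vs 0-1 |

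The inactive group is the remission definition. The active group is the union of the mild, moderate and severe total-score grades.

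**Count of score patterns.** Inputs, from Section 7.7.2.2: four subscores, each 0 to 3, giving 4 × 4 × 4 × 4 = 256 patterns.

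1. Total ≤2: 1 pattern sums to 0, 4 sum to 1 and 10 sum to 2, so 15.
2. Inactive (total ≤2, every subscore ≤1): 1 + 4 + 6 = 11. None has an endoscopy subscore of 2 or more.
3. In neither group (total 2 from a single subscore of 2): 15 − 11 = 4, one for each item. One of them is endoscopy 2 with the other items 0.
4. Active (total >2): 256 − 15 = 241.
5. The 241 by endoscopy subscore. There are 64 patterns at each level.
   - Endoscopy 0: the other three items sum to ≤2 in 1 + 3 + 6 = 10, leaving 64 − 10 = 54.
   - Endoscopy 1: the other three sum to ≤1 in 1 + 3 = 4, leaving 64 − 4 = 60.
   - Endoscopy 2 or 3: 63 + 64 = 127.
   - Check: 54 + 60 + 127 = 241.

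So 54 + 60 = 114 of the 241 patterns that the endpoint calls endoscopically active have an endoscopy subscore of 0 or 1, which Section 7.7.2.2 counts as mucosal healing. The count shows what the rule permits. It is unweighted and says nothing about how often each pattern occurs.

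One of the four unclassified patterns is awkward for the label: a subject with endoscopy 2 and nothing else is active under Section 7.7.3.2, yet belongs to neither group in Section 7.7.3.3.

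**The case against.** The best reply is that this is a stray adjective. Both sections state the same numeric rule, visits and comparator, so an analyst working from either forms the same groups. The comparator is called only inactive, never endoscopically inactive. Bullet order in both sections places these comparisons with clinical activity. Any endoscopic conclusion can rest on the separate analyses against the 0-3 endoscopic score. All of this stands, and it keeps the point minor. It does not remove it: the word sits in an endpoint definition, and bullet order suggests the intent without settling it.

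A second reply concerns the threshold. Section 7.7.2.2 grades an endoscopy score of 1 as mild disease, so calling such a subject endoscopically active is not plainly wrong on that scale. The split at 2 comes from an ST2 secondary endpoint, and the Section 8.0 sentence tying endoscopic activity to the subscore sits in the week-6 ST2 ROC paragraph. This stands in part. Only endoscopy 0 (54 patterns) conflicts with the label under every reading; the 60 patterns with endoscopy 1 conflict with the 0-1 rule.

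Stronger readings that the documents do not support:

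- **A head count.** A reader might subtract the 18% remission rate from the 42% healing rate cited in Section 5.1 and infer that about (0.42 − 0.18) × 37 = 8.9 subjects would be mislabelled at week 6. Those rates belong to another study, and healing there, on this protocol's definition, would pool scores 0 and 1, so the clearly mislabelled group cannot be separated. There are no corresponding week-16 rates.
- **The unclassified pattern is rare.** Appendix 3 says that the global assessment takes the other items into account, but also other observations. It does not fix how it is scored, so no frequency follows.
- **The planned tests are wrong.** If clinical activity was meant, the Section 8.0 groups already express it, apart from the unclassified subjects.

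**Conclusion.** The point holds as a minor inconsistency in two exploratory endpoints. The label says endoscopic; the rule is total Mayo above 2 against clinical remission; Section 8.0 repeats the rule without the label. Under the label, subjects with endoscopy 0 and a total above 2 would be misdescribed on any reading, and those with endoscopy 1 would be misdescribed under the 0-1 rule. Separately, 4 of 256 patterns fall in neither group in both sections.

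The numbers of subjects misdescribed or unclassified cannot be derived from the documents. The analysis as currently specified forms the same groups from either section, so the label alone alters no result; it alters what the result is said to show. The primary and secondary endpoints are unaffected. The conclusion rests on the definitions as written and on no assumption about event rates. Clinical activity is the likelier intent, but only the sponsor can confirm that.

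**What to change.** Before analysis, the sponsor states which comparison is intended and aligns Sections 7.7.3.3 and 8.0.

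- **If clinical activity is meant:** delete the word endoscopic from the two bullets in Section 7.7.3.3, and in both sections define active as all subjects not in remission at that visit. Everyone assessed is then classified. The comparison becomes identical to the remission comparison already planned and should be reported as that one, not as an additional finding. The only change to the data analysed is that the unclassified subjects join the active group.
- **If endoscopic status is meant:** in both sections use an endoscopy subscore of 2 or more versus 0 or 1 at the same visit, as in Section 7.7.3.2. This regroups subjects and changes the groups tested in Section 8.0.

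The cost is an edit to four bullets, two in each section, and a recorded decision by the sponsor. No new data are needed.

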## 7.8 Criteria for Early Termination of the Trial

There are no pre-specified criteria for terminating the trial early.

In addition, further recruitment in the trial or at (a) particular site(s) may be stopped due to insufficient compliance with the protocol, GCP and/or other applicable regulatory requirements, procedure-related problems, or the number of discontinuations for administrative reasons is too high.

## 8.0 STATISTICAL AND ANALYTICAL PLAN

All quantitative variables will be summarize through descriptive statistics namely mean, median, standard deviation and range (minimum and maximum) and qualitative variables though absolute (n) and relative frequencies (%) and 95% confidence intervals (if applicable). The statistical analysis will be performed through frequency tables for qualitative variables and tables with descriptive statistics for quantitative variables.

The association between two quantitative variables will be performed through Pearson correlation coefficient or Spearman correlation coefficient, in case the normality assumption was not verified.

The association of two categorical variables will be tested through the Chi-Square test or Fisher Exact test (if applicable). Cohen's kappa coefficient will be performed.

The comparison of two independent samples in respect to quantitative variables will be performed through t-test for independent samples or the Mann-Whitney non-parametric test, according to the assumption validations of the statistical test.

ROC curve analysis will be performed as well as sensitivity, specificity, and positive and negative predictive values.

The primary analysis is to investigate the correlation between serum soluble ST2 and:

- endoscopic activity of disease (measured by Endoscopy Mayo subscore) at 6 weeks in UC subjects receiving golimumab, through the Spearman correlation coefficient;
- histological activity (measured by Geboes index score) at 6 weeks in UC subjects receiving golimumab, through the Spearman correlation coefficient.

Additionally, it will be obtained the cut-off of serum soluble ST2 levels at week 6 that optimizes sensitivity and specificity in the identification of disease activity through ROC curve analysis supplemented with analysis of sensitivity, specificity, and positive and negative predictive values. Endoscopic activity will be classified according to endoscopy subscore of Mayo score and histological activity will be classified according to Geboes index score.

For the analysis of the secondary endpoints the following analysis will be performed:

- the correlation between serum soluble ST2 with endoscopic activity of disease (measured by Endoscopy Mayo subscore) at 16 weeks in UC subjects receiving golimumab, through the Spearman correlation coefficient;
- the correlation between serum soluble ST2 histological activity (measured by Geboes index score) at 16 weeks in UC subjects receiving golimumab, through the Spearman correlation coefficient.
- Correlations will also be performed between serum soluble ST2 levels and endoscopic and histological activity at baseline.
- Serum soluble ST2 levels at baseline, Week 6 and Week 16 will be correlated with fecal calprotectin levels at baseline, week 6 and week 16 through Pearson correlation coefficient or Spearman correlation coefficient in case the normality assumption was not verified. The two biomarkers will be categorized by the cut-offs and Cohen's kappa coefficient will be obtained.

- Serum soluble ST2 levels at baseline, week 6 and week 16 will be correlated with clinical activity (total Mayo score), through Spearman correlation coefficient.
- Comparative analyses of means (active disease versus inactive disease at week 6) with serum ST2 at baseline and change between baseline and week 6.
- Comparative analyses of subjects who achieved response at week 6 and maintained through week 16 versus subjects who did not maintain response, regarding serum soluble ST2 at baseline, week 6 and change between baseline and week 6. ROC curve analysis of the serum soluble ST2 at week 6 regarding maintenance of response between week 6 and 16 will be performed. This exploratory analysis will detect the cut-off levels of the serum soluble ST2 at week 6 associated with maintenance of response.
- It will be investigated the correlation of Mayo endoscopic score at baseline, week 6 and week 16 with UCEIS overall score at baseline, week 6 and week 16, through the Spearman correlation coefficient.

For the exploratory endpoints the following analysis will be performed:

- Serum golimumab levels at week 6 and week 16 will be correlated with clinical activity (total Mayo score) at the same time points, through Spearman correlation coefficient.
- Mean serum golimumab levels will be compared between patients with active disease (total Mayo score  $>2$ ) and patients with inactive disease (total Mayo score  $\leq 2$  points with no individual subscore  $> 1$ ) at week 6 and 16 through T-test for independent groups or Mann-Whitney test according to the assumption validations of the statistical test.
- The association between the presence of anti-golimumab antibodies at week 6 and week 16 and clinical activity (total Mayo score) at the same time points will be tested through t-test for independent samples or the Mann-Whitney non-parametric test, according to the assumption validations of the statistical test.
- Presence of anti-golimumab antibodies will be compared between patients with active disease (total Mayo score  $>2$ ) and patients with inactive disease (total Mayo score  $\leq 2$  points with no individual subscore  $> 1$ ) at week 6 and 16 through Chi-Square test or Fisher exact test.
- Serum golimumab levels at week 6 and week 16 will be correlated with endoscopic activity (endoscopic Mayo score) at the same time points, through Spearman correlation coefficient.

- The association between the presence of anti-golimumab antibodies at week 6 and week 16 and endoscopic activity (endoscopic Mayo score) at the same time points will be tested through t-test for independent samples or the Mann-Whitney non-parametric test, according to the assumption validations of the statistical test.
- Serum golimumab levels at Week 6 and Week 16 will be correlated with faecal calprotectin levels at the same time points through Pearson correlation coefficient or Spearman correlation coefficient in case the normality assumption was not verified.
- The association between the presence of anti-golimumab antibodies at Week 6 and Week 16 and faecal calprotectin levels at the same time points will be tested through will be tested through t-test for independent samples or the Mann-Whitney non-parametric test, according to the assumption validations of the statistical test.

Both measurements will be categorized by the cut-offs and Cohen's kappa coefficient will be obtained.

- The correlation between serum golimumab levels at week 6 and 16 and histological activity (measured by Geboes index score) at the same time points will be performed through the Spearman correlation coefficient.
- The association between the presence of anti-golimumab antibodies at week 6 and 16 and histological activity (measured by Geboes index score) at the same time points will be tested through Mann-Whitney non-parametric test.
- Subjects who achieved response / remission at week 6 versus subjects who did not will be compared regarding serum golimumab levels at this time point through T-test for independent groups or Mann-Whitney test according to the assumption validations of the statistical test.
- Subjects who achieved response / remission at week 16 versus subjects who did not will be compared regarding serum golimumab levels at this time point through T-test for independent groups or Mann-Whitney test according to the assumption validations of the statistical test.
- Subjects who achieved response / remission at week 6 versus subjects who did not will be compared regarding the presence of anti-golimumab antibodies at this time point through the Chi-Square test or Fisher Exact test (if applicable).
- Subjects who achieved response / remission at week 16 versus subjects who did not will be compared regarding the presence of anti-golimumab antibodies at this time point through the Chi-Square test or Fisher Exact test (if applicable).

- ROC curve analysis of the serum golimumab levels at week 6 regarding maintenance of response between week 6 and 16 will be performed. This exploratory analysis will allow to detect the cut-off for serum golimumab levels at week 6 associated with maintenance of response.

In addition, CRP at baseline, week 6 and week 16 will be correlated with endoscopic activity (measured by Endoscopy Mayo subscore) and histological activity at the same time points, through Spearman correlation coefficient.

Bivariate correlation analysis will be carried out for ST2, calprotectin, CRP and endoscopy Mayo score.

The incidence of adverse events (percentage of subjects with at least one adverse event) and serious adverse events (overall and with reasonable relationship) will be presented as well as the frequency distribution of AEs and SAEs (overall and with reasonable relationship) by means of total number of observations (n) and relative frequency (%). Frequency distribution of adverse events by grade and relationship with study drug will be summarized by total number of observations (n) and relative frequency (%).

Adverse events will be listed individually with severity, grade, relationship with study drug, duration (for solved AEs and calculated as the difference between end date and start date), measures taken and outcome.

All deaths will be listed, regardless of being caused by adverse events.

Results for hematology (basophils, eosinophils, hematocrit, hemoglobin, lymphocytes, monocytes, neutrophils, platelets, RBC, WBC); blood chemistry (total bilirubin, ALT, AST, alkaline phosphatase, albumin, total protein, calcium, phosphate, sodium, potassium, chloride, urea and creatinine and CRP; urinalysis (proteins, glucose, nitrates, WBC, ketone bodies, hemoglobin, urobilinogen, bilirubin) will be summarized by total number of observations (n), mean, median, standard deviation, minimum and maximum.

Based on the recruitment capacity of sites it is expected to include a total of 37 subjects for analysis. With this sample size there is a probability of 80% that the lower limit of a one-sided 95% confidence interval is higher than 0.50, if the observed correlation coefficient is at least 0.75.

The primary analysis is to be performed on the Full Analysis Set, defined as all subjects who had received study medication and had at least one valid post baseline assessment for the primary endpoint that correlates ST2 with endoscopic activity.

In addition, a Per Protocol Set is defined as subjects receiving study medication, who meet key eligibility and evaluability criteria (without major protocol deviations). Sensitivity analyses will be based on this Per Protocol Set.

All safety analyses will be performed on the All Treated Set, comprising all subjects who received at least one dose of study medication.

No interim analysis is planned.

